Patients must be >18 years old and able to give informed consent.

For the provider surveys and interviews, all providers (clinicians, trainees) who are working on the project will be eligible to participate. There is no obligation to participate in the study and this will be explained via the research letter included in Section S.

Exclusion Criteria:

- Allergy or prior reaction to the fluorescent contrast agent proflavine - Patients who are unable to give informed consent - known advanced squamous cell carcinoma of the distal esophagus, or dysplastic/suspected malignant esophageal lesion greater than or equal to 2cm in size not amenable to endoscopic therapy - Patient unable to undergo routine endoscopy with biopsy: - women who are pregnant or breastfeeding - prothrombin time greater than 50% of control; PTT greater than 50 sec, or INR greater than 2.0 - inability to tolerate sedated upper endoscopy due to cardio-pulmonary instability or other significant medical issues

For the provider surveys and interviews, all providers (clinicians, trainees) who are working on the project will be eligible to participate. There is no obligation to participate in the study and this will be explained via the research letter included in Section S. Providers will be excluded if they decline participation or otherwise opt out of the proposed research project.

F2. Procedure

[name] will accrue subjects (n=50) already scheduled for endoscopic screening due to a high risk for ESCC (head and neck cancer history; heavy smoking and alcohol, other dietary or geographic risk factors). Lugol's chromoendoscopy (LCE) is the current standard of care for esophageal cancer screening.

To uphold this standard of care and recruit patients already scheduled for endoscopy, LCE will be performed on all patients, followed by marHRME of Lugol's voiding (unstained areas). Subjects will be sedated per standard protocol (IV sedation) and undergo white-light endoscopy with application of Lugol's iodine. In each subject, the location of each Lugol's unstained area (level, quadrant) will be recorded and digital images obtained. The endoscopist's clinical impression will be recorded for each Lugol's abnormal area and visible lesions ('non-neoplastic' vs. 'neoplastic') as well as his/her proposed plan: a. no biopsy, b. biopsy, c. endoscopic treatment.

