Expert clinicians will be defined as any clinician with prior microendoscopy experience (>25 procedures) and novices are clinicians without any prior experience. We will collect this information in the CRF and compare outcomes between the 2 groups of clinicians. The clinician will give a \checkmark read \checkmark (Neoplastic/Non neoplastic) and \checkmark plan \checkmark (Biopsy/No Biopsy/Ablate/ESD/EMR) at several timepoints: 1- Based solely on Lugol's (SOC), 2- Using HRME with no software (Qualitative Read), and 3- After software overlay (Quantitative Read). The marHRME output is a numerical score (quantitative). Based on this score, clinicians may change their plan for the lesion. For ex: if they read the image without the overlay and aren't sure if they should biopsy, a high (neoplastic) score may increase confidence in their decision to biopsy, or a low (non-neoplastic) score may increase confidence to not biopsy the area.

Section G: Sample Size/Data Analysis

G1. Sample Size

How many subjects (or specimens, or charts) will be used in this study?

Local: 0 Worldwide: 50

Please indicate why you chose the sample size proposed:

We will collect an average of 2-3 biopsies/subject in screening patients. All patients will have biopsies and their pathological diagnosis will be used to measure the accuracy of LCE and marHRME (man and machine). As mentioned, LCE has a sensitivity of > 95% but a specificity of <65% due to a high-false positive rate (82%) resulting in a low diagnostic yield (unnecessary benign biopsies) and, subsequently, increased cost. Our hypothesis is that the addition of marHRME to LCE will increase the accuracy, efficiency of marHRME, and clinical impact, particularly for novice endoscopists while increasing confidence levels in novice and experts. Based on the preliminary data, the accuracy of marHRME vs LCE was 83% (CI: 76-89%) vs 47% (CI: 39-55%). A sample size of 50 subjects will provide 87% power to detect a 35 % improvement in accuracy (80% for marHRME vs 45% for LCE) with a 5% two-sided significance level and 0.7 discordant pairs using McNemar's test for the paired data.

G2. Data Analysis

Provide a description of your plan for data analysis. State the types of comparisons you plan (e.g. comparison of means, comparison of proportions, regressions, analysis of variance). Which is the PRIMARY comparison/analysis? How will the analyses proposed relate to the primary purposes of your study?

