Data of accuracy, sensitivity, specificity, positive predictive value (PPV), and negative predictive value (NPV) for each method will be summarized using proportions and 95% confidence intervals, and compared using McNemar's tests. Our primary study endpoint is accuracy. Other exploratory endpoints include: Clinician confidence and clinical impact (decision

plan change: biopsy vs. not biopsy vs. treat) that will be summarized and presented in a cross table of pre/post software read. These parameters between expert and novice endoscopists will also be summarized descriptively. Biopsy saving and diagnostic yield will be calculated and presented with proportions and their 95% confidence intervals. Assuming a 80% response rate, we anticipate that 40 patients will complete the survey. We will describe the prevalence of specific barriers to endoscopy with confidence intervals around the point estimate. Descriptive statistics will be used to identify experiences of participants undergoing marHRME endoscopy. Associations with $p < 0.05$ will be considered statistically significant.

Section H: Potential Risks/Discomforts

H1. Potential Risks/Discomforts

Describe and assess any potential risks/discomforts; (physical, psychological, social, legal, or other) and assess the likelihood and seriousness of such risks:

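### McNemar's test cannot compare PPV or NPV: on the shared sites it is 0/0, and on all sites its p-value is the accuracy p-value

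*Combined protocol and SAP*

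**What the plan says.** The analysis sentence in G2 (Data Analysis) opens with "Data of accuracy, sensitivity, specificity, positive predictive value (PPV), and negative predictive value (NPV") and ends by having all of these "negative predictive value (NPV) for each method will be summarized using proportions and 95% confidence intervals, and compared using McNemar's tests". No other section names a test for PPV or NPV, and G2 does not say which sites enter each comparison. G2 also sets p < 0.05 as the level at which associations "will be considered statistically significant".

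The primary role is clear: "Our primary study endpoint is accuracy". The only powered comparison is in G1 (Sample Size), which claims "87% power to detect a 35 % improvement in accuracy (80% for marHRME vs 45% for LCE"). That calculation is for McNemar's test, two-sided at 5%, and takes 0.70 of the pairs to be discordant.

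On the data, G1 says of the biopsies that "their pathological diagnosis will be used to measure the accuracy of LCE and marHRME (man and machine"), so every read at a site is judged against one histology result. F2 (Procedure) has the endoscopist give a neoplastic or non-neoplastic read on Lugol's chromoendoscopy (LCE) alone, then on the microendoscope (marHRME) without software, then with software. For the LCE step, the "clinical impression will be recorded for each Lugol's abnormal area and visible lesions".

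**The concern.** McNemar's test compares two paired proportions taken over the same units. Accuracy uses all sites, sensitivity the neoplastic sites and specificity the benign sites. In each case histology or the whole sample fixes the denominator, so both methods share it. PPV is computed over the sites a method calls positive and NPV over the sites it calls negative, so the two methods have different denominators.

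An analyst who follows G2 literally therefore gets either an undefined statistic or a p-value for another quantity. The second outcome is the harmful one, because it looks like a valid result. NPV also matters in this study: F2 treats marHRME non-neoplastic sites as not biopsied for the analysis, and Section D aims to reduce biopsies. A spurious significant gain in NPV would bear directly on whether biopsy could be omitted.

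**Working it through.** **1. The plan's own figure.** Inputs from G1: n = 50, difference d = 0.80 − 0.45 = 0.35, discordant proportion 0.70, two-sided 5%. The discordant cells are (0.70 + 0.35)/2 = 0.525 and (0.70 − 0.35)/2 = 0.175.

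Power = Φ[(d√n − 1.96√0.70) / √(0.70 − d²)] = Φ[(2.475 − 1.640)/0.760] = Φ(1.10) = 86.4%.

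Full enumeration without continuity correction gives 87.0%. G1's 87% is reproduced.

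**2. Algebra, with no numerical assumption.** Both reads are binary and each site has one histology result.

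- *Sites positive on both methods* are the only sites in both PPV denominators. The two reads are the same, so both are right or both wrong. The discordant counts are b = c = 0, and (b − c)²/(b + c) is 0/0. The same holds for NPV on sites negative on both.
- *Sites where the reads differ.* Exactly one method is right, so every such site is a discordant pair for accuracy. McNemar on correctness over all sites, over sites positive on either method, or over sites negative on either method uses the same b and c. Each version returns the accuracy p-value.
- *Neoplastic sites only* give the sensitivity test, and *benign sites only* the specificity test.
- *Pairing the positive/negative calls over all sites*, instead of correctness, tests equal positivity rates.

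None of these is a test of PPV or NPV.

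**3. Size of the mislabelling.** This example is built so that the true NPV difference is zero while G1's accuracies and discordance are kept. Assumptions: LCE sensitivity 95%, and LCE specificity 18% (G1's 82% false-positive rate read as 1 − specificity).

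- Prevalence among analysed sites: (0.45 − 0.18)/(0.95 − 0.18) = 0.351.
- LCE NPV: 0.18 × 0.649 / (0.18 × 0.649 + 0.05 × 0.351) = 0.870.
- Equal NPV requires the same ratio (1 − sensitivity)/specificity: 0.05/0.18 = 0.278.
- With accuracy 0.80, marHRME specificity = (0.80 − 0.351)/(0.649 − 0.278 × 0.351) = 0.814, and sensitivity = 1 − 0.278 × 0.814 = 0.774. Its NPV is also 0.870.
- The largest discordance possible is 0.351 × (0.05 + 0.226) + 0.649 × (0.18 + 0.814) = 0.742, so 0.70 is feasible.

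Expected counts in one set of 50 sites with this structure:

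| | both right | marHRME only right | LCE only right | both wrong |
|---|---|---|---|---|
| Neoplastic | 12.89 | 0.68 | 3.77 | 0.20 |
| Benign | 0.86 | 25.57 | 4.98 | 1.05 |

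LCE NPV = (0.86 + 4.98)/(0.68 + 0.20 + 0.86 + 4.98) = 5.84/6.72 = 0.87. marHRME NPV = (0.86 + 25.57)/(3.77 + 0.20 + 0.86 + 25.57) = 26.43/30.40 = 0.87. Yet b = 0.68 + 25.57 = 26.25 and c = 3.77 + 4.98 = 8.75, so McNemar on the expected counts is 17.5²/35 = 8.75, well above 3.84.

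Proportion of trials in which all-site McNemar gives p < 0.05 (enumeration, treating sites as independent):

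| Pairs | 50 | 100 | 125 | 150 |
|---|---|---|---|---|
| Rejection | 87.0% | 99.3% | 99.8% | >99.9% |

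The range 100 to 150 is 50 subjects × the 2 to 3 biopsies in G1.

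**4. Other assumed values.** With LCE sensitivity 95% and the same two accuracies, equal NPVs also exist at prevalence 30% (LCE specificity 23.6%, NPV 91.7% for both) and 20% (LCE specificity 32.5%, NPV 96.3% for both). No solution was found at LCE specificity 10%.

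**5. Alternatives checked.** Simulations used 50 subjects with 2 to 3 sites each, equal true NPVs, prevalence 20%, 30% or 35%, histology intraclass correlation 0 or 0.2, and reads independent given histology.

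- The weighted generalized score test for NPV rejected in 3.6 to 4.3% of trials.
- A percentile bootstrap by subject wrongly excluded zero for NPV in 9 to 16%, with only 17 to 34 LCE-negative sites per trial.
- The same bootstrap covered the PPV difference in 93 to 94%.
- In the section 3 scenario, with independent sites, a simple paired Wald test for NPV rejected in 23% of trials at 50 sites and 13% at 125.

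**The case against.** The strongest reply accepts the algebra and disputes the weight. This is a pilot of 50, accuracy is the only powered endpoint, and PPV and NPV appear in no stated hypothesis. Diagnostic yield, the nearest objective, gets only proportions and intervals in G2. All of that stands, and it limits the point to secondary analyses.

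The 87% can also be called constructed. It is the accuracy test's power under another name, and marHRME's sensitivity and specificity were solved for. This is correct: the rejection rate depends only on accuracy and discordance, so its constancy across prevalences is not a sensitivity analysis. The 82% might also mean something other than 1 − specificity. The example shows that the error can reach that size, not that it will. G2 never says an NPV test would be run on all sites, and an analyst would notice 0/0. But G2 names no usable alternative either.

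Finally, the documents conflict on whether Lugol's-normal areas are biopsied: F1 includes them, while F2 limits biopsy to abnormal areas. If an LCE positive meant simply unstained, the F2 rule would leave LCE with no NPV denominator. F2, however, records a neoplastic or non-neoplastic LCE read at the unstained areas, so LCE-negative reads with histology can occur. Neither reading makes McNemar a test of NPV.

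**Conclusion.** The concern holds. G2 explicitly assigns to PPV and NPV a test that cannot compare them; this is a wrong rule, not a missing detail. That conclusion rests only on binary reads judged against one histology result per site.

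If the all-site test were labelled as NPV, the false-positive rate could be 87% with 50 pairs and above 99% with 100 to 150, under the assumptions in the worked example. The primary accuracy comparison, G1's power figure and the planned 95% intervals for PPV and NPV are not affected by this point. It should be corrected before analysis, but it does not threaten the main result.

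**What to change.** Replace the G2 sentence with wording such as:

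> *Accuracy, sensitivity and specificity will be compared between methods with McNemar's test. PPV and NPV will be reported for each method with 95% confidence intervals; any p-value for them will come from a weighted generalized score test for paired predictive values, with sites clustered by subject.*

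Reporting the intervals without a p-value is enough for a pilot. If a test of NPV is wanted, avoid a simple paired Wald test or a percentile bootstrap, since both reject too often when few sites are LCE-negative. A subject-level bootstrap interval is reasonable for the PPV difference. Whether the McNemar tests should also allow for several sites per subject is a separate question, which can be settled in the same edit.

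The cost is one sentence and standard code, with no new data and no change to the sample size.

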
Section D: Purpose and Objectives

We have a current trial in China and the US which provides significant support for the safety, cost-effectiveness, accuracy and efficiency of a high resolution microendoscope (HRME)-guided approach in the hands of experienced clinicians. To improve functionality, portability and broader use of this device by non-experts, we recently developed a prototype marHRME platform with an automated, augmented reality (AR)-interpretation that provides an overlaid endoscopic + micro-endoscopic view, facilitating diagnosis and biopsy targeting. Our hypothesis is that this mobile device with automated, AR optical biopsy diagnoses can efficiently and accurately facilitate endoscopic cancer detection in LMICs with less experienced providers and is acceptable to providers and patients. Objective 1: Our first objective is to evaluate the marHRME technology in terms of performance, efficiency, and impact. In a single-arm, feasibility study (n=50) of high-risk subjects undergoing Lugol's chromoendoscopy (LCE) followed by marHRME for ESCN screening, we will evaluate the diagnostic performance and efficiency of this automated optical biopsy device. Our main hypothesis is that the marHRME will (1) increase the accuracy of Lugol's endoscopy (LCE), other exploratory hypotheses are (2) increase the accuracy of marHRME among novices and be non-inferior to experts, (3) increase user confidence among experts and novices and, subsequently, (4) increase the efficiency and impact of LCE by reducing biopsies and second procedures. For performance for marHRME vs. Standard of Care, we will compare the accuracy of the marHRME + LCE vs. LCE alone to the gold-standard histopathology (expert GI pathologist). For performance of the Machine vs. Man, we will compare accuracy of the marHRME software read to novice and expert clinicians' subjective read to gold-standard histopathology. For clinician confidence and clinical impact, we will determine the clinician's confidence level in the software diagnosis and the potential clinical impact of this diagnosis among novice and expert endoscopists using marHRME. Clinical impact will be determined by whether the marHRME diagnosis alters the clinician's decision at the point-of-care to biopsy vs. not biopsy vs. treat the visualized site. For efficiency (biopsy saving and diagnostic yield), we will determine the number of patients who are spared any biopsy due to marHRME. We will compare the diagnostic yield of marHRME+LCE vs. LCE alone (diagnostic yield= neoplastic biopsies/total number of biopsies obtained in biopsied patients). Objective 2: Our secondary objective is to evaluate the acceptability of the technology among patients and providers. All patients participating in the study will be invited to participate in a brief (20 min) interviewer-administered survey prior to undergoing endoscopy to assess attitudes and barriers to marHRME (T1), and a follow-up interview (7 days post-procedure) to determine experiences and acceptability (T2). Informed consent and the initial interview will be conducted in a private clinic room by trained study staff from the Brazilian team using a brief Portuguese-language survey. The follow-up interview will occur by phone, after a routine follow-up call by clinical staff. The endoscopists and trainees participating in the feasibility study will be invited to participate in a series of questionnaires and in-depth interviews administered at different time points of the study to assess provider acceptance. Informed consent will be obtained prior to the first interview. Clinicians will answer a brief questionnaire to assess acceptance of marHRME prior to undergoing training (T1), after training (T2), and after conducting 25 procedures (T3). At T3, endoscopists and trainees will participate in a 30-minute semi-structured interview to assess marHRME experience. The interviews will be audio recorded, professionally transcribed, and

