Subsequently, marHRME will be performed of all Lugol's unstained (abnormal) sites prior to tissue biopsy. The endoscopist will activate the marHRME glasses and marHRME performed: (1) 1-10 ml proflavine hemisulfate (0.01%) will be sprayed on the esophageal mucosa, (2) the marHRME probe placed gently on the Lugol's abnormal areas, (3) the 'optical biopsy' image will be displayed on the AR glasses (endoscopic image will remain displayed on the standard monitor behind it). (Proflavine is used under an IND #102217).

The endoscopist will FIRST make a subjective interpretation ('non-neoplastic' vs. 'neoplastic'), record their confidence level in the diagnosis (high confidence vs. low confidence), and indicate their plan of action (a. biopsy, b. no biopsy, c. treat). All of this will be done WITHOUT the image-analysis software.

Once this qualitative read is recorded, the image analysis software will be turned on (foot pedal) and the software diagnosis provided in real-time with display on the AR glasses. The quantitative ("Machine") read will be recorded, the confidence level of the endoscopist obtained again, and the (revised) plan of action recorded (a numerical score). The software output (score) will be determined neoplastic (cancer) or non-neoplastic (normal) based on a predetermined

algorithm threshold. This quantitative read may influence clinician read, plan, and confidence.

The HRME procedure (including "man" and "machine" reads), standard endoscopy and biopsy time will be recorded. The research coordinators will indicate the biopsy number/location on an esophageal map diagram. The biopsies from each site will be placed in formalin per standard-of-care and labeled according to biopsy location (quadrant: 12, 3, 6, 9 o'clock).

In all subjects, all Lugol's abnormal areas will be biopsied (to uphold the standard of care); however, HRME "non-neoplastic" sites will be considered not tissue-biopsied for purpose of the analysis. All biopsies will be submitted for consensus diagnosis by an expert GI pathologist. All patient adverse events (bleeding, infection, perforation) that occur within 7 days after the procedure will be recorded on follow up call.

It is very possible that the HRME will increase the accuracy of standard Lugol's screening and may reduce unnecessary biopsies by improving specificity. With novices, the HRME + computer algorithms may be very likely to improve accuracy and performance, based on our preliminary data from China.

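### G2 does not state the unit of accuracy or any method for the 2-3 biopsied sites per subject; pooling sites in a standard McNemar test could push type I error above 5%

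*Combined protocol and SAP*

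**What the plan says.** - **Analysis (G2, Data Analysis).** Accuracy, sensitivity, specificity, PPV and NPV "for each method will be summarized using proportions and 95% confidence intervals, and compared using McNemar's tests". Accuracy is named as the primary endpoint. No unit, clustering method or combining rule is given.
- **Yield (G2 and Section D).** "Biopsy saving and diagnostic yield will be calculated and presented with proportions and their 95% confidence intervals". Section D defines the measure per biopsy: "diagnostic yield= neoplastic biopsies/total number of biopsies obtained in biopsied patients".
- **Data level (F2, Procedure).** The endoscopist's "clinical impression will be recorded for each Lugol's abnormal area". The marHRME reads are also made on individual areas. For histology, "The biopsies from each site will be placed in formalin per standard-of-care and labeled according to biopsy location". F2 also gives an analysis convention in terms of sites: those that HRME reads as non-neoplastic count as not biopsied.
- **Number of sites (G1, Sample Size).** "We will collect an average of 2-3 biopsies/subject in screening patients".
- **Power (G1).** "A sample size of 50 subjects will provide 87% power to detect a 35 % improvement in accuracy", from 80% against 45%, two-sided 5%, 0.7 discordant pairs, McNemar's test.

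**The concern.** The plan collects about 100-150 paired site results from 50 people, but counts people in its power statement and names no unit in its analysis. The primary test can therefore be run in two ways, and the text does not choose.

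If sites are pooled, a standard McNemar test treats sites from one subject as independent. With positive within-subject correlation in the paired difference, it rejects too often and the interval for the difference is too narrow. If one result per patient is meant, McNemar's test is valid, but the endpoint has no definition: a patient with three sites, two read correctly, is neither right nor wrong under any stated rule. It is also unknown whether 80%, 45% and 0.7 discordance apply at patient level.

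A unit left open can also be settled after the results are known. For yield the unit is clear, but a standard binomial interval over all biopsies would be too narrow if outcomes cluster by subject.

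**Working it through.** **1. Reproduce the 87%.** Inputs from G1: n = 50, difference 0.35, discordance 0.7. Then p10 = (0.7 + 0.35)/2 = 0.525 and p01 = (0.7 − 0.35)/2 = 0.175. Enumerating the uncorrected McNemar chi-square test over Binomial(50, 0.7) discordant pairs gives 0.870, which matches. The exact version gives 0.826. The stated figure thus refers to 50 independent pairs, one per subject.

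**2. Do the preliminary data settle the unit?** G1 reports 83% (76-89%) against 47% (39-55%). Ordinary binomial intervals reproduce both at a common n of 145-160 (Clopper-Pearson), 130-144 (Wilson) or 134-149 (Wald). G1 does not say whether those units are sites or patients, so the question stays open.

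**3. Type I error if sites are pooled.** The ICC of the paired difference is assumed. With m sites per subject, the design effect is 1 + (m − 1) × ICC, and the actual level is about 2 × [1 − Φ(1.96/√design effect)]. For m = 2 and ICC 0.3 the design effect is 1.3 and the level about 8.6%. For m = 3 and ICC 0.5 it is 2.0 and about 16.6%.

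Simulation under the null (50 subjects, p10 = p01 = 0.35, 20,000 trials per setting), pooled uncorrected McNemar:

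| Sites per subject | ICC 0 | 0.1 | 0.3 | 0.5 |
|---|---|---|---|---|
| 2 | 4.7% | 6.3% | 8.7% | 11.2% |
| 2-3 mix | 4.9% | 6.7% | 11.0% | 14.8% |
| 3 | 4.9% | 7.4% | 12.4% | 16.6% |

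A second simulation with a different correlation model (Dirichlet-multinomial) gave 6.1-7.5%, 8.4-12.3% and 10.8-16.7% at ICC 0.1, 0.3 and 0.5. The pooled exact test was less inflated, about 5.2-15.5% over the same range. A subject-clustered McNemar test stayed at 4.6-5.2% throughout.

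**4. Interval for the accuracy difference.** The naive width relative to the correct width is 1/√design effect. At ICC 0.1/0.3/0.5 this is 95/88/82% with 2 sites and 91/79/71% with 3. Simulated coverage of the nominal 95% interval at the planned effect was 93.2/90.6/88.6% and 92.3/87.3/82.3%; clustered intervals covered 94.6-95.2%.

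**5. Diagnostic yield.** Assumptions: 18% yield (reading G1's 82% as the share of benign biopsies) and all 50m biopsies counted. Half-width = 1.96 × √[0.18 × 0.82 × (1 + (m − 1) × ICC)/(50m)], where the ICC is that of the biopsy outcome.

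| Biopsies per subject | Unadjusted | ICC 0.3 | ICC 0.5 |
|---|---|---|---|
| 2 | 7.5 points | 8.6 | 9.2 |
| 3 | 6.1 points | 7.8 | 8.7 |

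**6. Is power harmed?** Adjusted z = 0.35/√[0.7 × design effect/(50m)]. From ICC 0 to 0.5 this runs from 4.18 to 3.42 with 2 sites and from 5.12 to 3.62 with 3. Simulated power of the clustered test was about 95% or more throughout. Even at ICC 1, equal clusters leave 50m/m = 50 effective pairs, the number on which G1 is based.

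**The case against.** **The patient may be the intended unit.** G1 counts subjects, its 87% reproduces only with one pair per subject, and its sentence on pathological diagnosis can be read as referring to the patient's diagnosis. On that reading there is no inflation. This has weight and makes the type I error conditional. It does not close the gap: F2 records reads by site and frames an analysis convention in sites, and no rule reduces several sites to one result.

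**The size is hypothetical.** The relevant ICC is that of the paired difference, which need not equal that of either method's accuracy. Nothing in the documents supports 0.5 over 0.1, and at 0 there is no inflation. This stands: the omission is certain, its numerical effect is not.

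**The yield figures show one side only.** Section D compares yield for marHRME+LCE with LCE alone, and F2 treats HRME non-neoplastic sites as not biopsied. The marHRME+LCE denominator would therefore be smaller and its yield different; neither is calculated here. The 18% also reinterprets a number that G1 calls a false-positive rate, and yield is exploratory. These points stand.

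**Stronger readings that a reader might infer.** One is that the primary test is invalid as planned; the documents do not say that sites will be pooled. Another is that the yield interval disregards clustering; G2 gives no interval method at all, so the fair statement is that none is specified. A third is that 50 subjects are too few; step 6 shows otherwise under G1's own assumptions.

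**Conclusion.** The point holds as an unstated unit with a conditional statistical consequence. G2 names neither the unit of its primary endpoint nor a method for several sites per subject, and no other section supplies one.

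If sites are pooled in a standard McNemar test and paired differences correlate positively within a subject, type I error is about 6-8%, 8-12% and 11-17% at assumed ICCs of 0.1, 0.3 and 0.5, and intervals are too narrow. If the patient is the unit, the test is valid but the endpoint is undefined. For yield, a standard binomial interval would be about 1.1-2.6 points too narrow in half-width at ICC 0.3-0.5, assuming 18% yield over all biopsies.

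An effect near the planned 35 points would remain significant after adjustment. What is at stake is the error rate when true differences are small, and the precision reported, which matters in a feasibility study. The study is classed as a pilot, so this should be fixed but does not threaten the design.

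**What to change.** 1. In G2, state the unit of accuracy.
2. If it is the site, use a subject-clustered McNemar test (Obuchowski or Durkalski) or a GEE with subject-robust standard errors. Use subject-clustered or subject-bootstrap intervals for accuracy, sensitivity, specificity, PPV and NPV.
3. If it is the patient, state the rule that combines sites into one result, and confirm that 80% against 45% and 0.7 discordance apply per patient.
4. In either case, use subject-clustered intervals for per-biopsy diagnostic yield, and state in G1 that 87% refers to 50 independent pairs.

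The cost is some wording in G1 and G2, a few lines of code and slightly wider intervals. No extra patients are needed if all 50 subjects contribute sites, as G1 expects.

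Separately, F1 describes biopsy or resection of the imaged areas, which include Lugol's-normal ones, while F2 limits biopsy to Lugol's-abnormal areas. These passages must be reconciled; the answer also sets the number of sites per subject.

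### The plan-change and confidence tables have no histology dimension, so they show the direction of a change but not whether it was right

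*Combined protocol and SAP*

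**What the plan says.** Section D (Purpose and Objectives) gives the definition: "Clinical impact will be determined by whether the marHRME diagnosis alters the clinician's decision at the point-of-care", the options being biopsy, no biopsy or treatment. Agreement of the new decision with histology is not part of it. The same section hypothesises that the device will "increase user confidence among experts and novices" and will increase the efficiency and impact of Lugol's chromoendoscopy. Section G1 repeats this as an expectation to "increase the accuracy, efficiency of marHRME, and clinical impact, particularly for novice endoscopists while increasing confidence levels in novice and experts". Neither statement is conditional on the diagnosis being correct.

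Section F2 (Procedure) describes the recording. After the microendoscope image, but before the software is switched on, endoscopists make their own read, "record their confidence level in the diagnosis (high confidence vs. low confidence"), and state a plan. The software result is then shown, and confidence and plan are recorded again. F2 acknowledges that "This quantitative read may influence clinician read, plan, and confidence". It also provides for tissue from every Lugol's-abnormal site, whatever the device shows.

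Section G2 (Data Analysis) makes accuracy the primary endpoint. It reports accuracy, sensitivity, specificity, PPV and NPV for each method with 95% confidence intervals and McNemar's tests. It then states "Other exploratory endpoints include: Clinician confidence and clinical impact (decision" plan change), "that will be summarized and presented in a cross table of pre/post software read", followed by a descriptive expert/novice summary. That is the whole analysis of these two endpoints.

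**The concern.** The value of a changed plan depends on what the site turns out to be. A move from biopsy to no biopsy is the intended saving at a benign site and a missed lesion at a neoplastic one. A move from low to high confidence is desirable when the diagnosis is right and undesirable when it is wrong. A table of pre-software against post-software plan puts each pair of opposites in one cell.

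The study hypothesises increases in both quantities, so a reader of the results will be inclined to take more change and more confidence as support. With the tables as described, that inference has no basis. At stake is the interpretation of two exploratory endpoints that bear on whether clinicians, novices in particular, make better decisions with the software.

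**Working it through.** **No planned figure for these endpoints.** The only stated figure nearby is the 87% power for the primary accuracy comparison in G1. It reproduces. With n = 50, difference 0.35, discordant proportion 0.7 and two-sided 5%, the normal approximation gives Φ[(0.35√50 − 1.96√0.7)/√(0.7 − 0.35²)] = Φ(1.10) = 86.4%. Exact enumeration of the uncorrected McNemar test gives 87.0%. Nothing below affects it.

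**Where histology is used.** G1 and G2 use histology for the accuracy measures, and section D uses it for diagnostic yield. No section links it to plan change or confidence, although F2 secures it at the same Lugol's-abnormal sites.

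**How common wrong reads would be on the plan's own assumptions.**

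1. At 80% accuracy (G1), 20% of marHRME reads are wrong. With 2–3 biopsies in each of 50 subjects (100–150 sites), that is 20–30 sites.
2. Discordance 0.70 and difference 0.35 imply marHRME right and Lugol's wrong in (0.70 + 0.35)/2 = 52.5% of pairs, and the reverse in (0.70 − 0.35)/2 = 17.5%. So 0.175/0.70 = 25% of discordant pairs move away from histology. Over the discordance possible with 80% and 45% (0.35 to 0.75), this share runs from 0% to 26.7%.
3. These figures compare marHRME with Lugol's, not reads before and after the software. They show that wrong-direction changes need not be rare, but they do not estimate the G2 table.

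**Illustration that more change need not mean better decisions.** Assumptions not in the documents: 125 sites (50 × 2.5), every plan being biopsy beforehand, the clinician always following the software, and prevalence of neoplasia at 18% or 35%. The 18% is one reading of the 82% false-positive figure in G1 (82% of sites benign). The 35% is another: (0.45 − 0.18)/(0.95 − 0.18) = 0.35, from sensitivity 95%, specificity 18% and accuracy 45%.

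Switches to no biopsy = TN + FN. At accuracy A with N sites and P neoplastic, TN = A·N − (P − FN), so switches = A·N − P + 2·FN. At fixed accuracy and prevalence, each further missed neoplasm adds two switches.

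| Prevalence | Sensitivity | TN | FN | Switches |
|---|---|---|---|---|
| 35% | 90% | 60.6 | 4.4 | 65 |
| 35% | 50% | 78.1 | 21.9 | 100 |
| 18% | 90% | 79.75 | 2.25 | 82 |
| 18% | 50% | 88.75 | 11.25 | 100 |

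All four rows have accuracy 80%. The less sensitive device gives 100/65 = 1.54, or 54% more switches, at 35% prevalence, and 100/82 = 1.22, or 22% more, at 18%. The comparison is not available at every prevalence: at 45%, sensitivity 50% allows accuracy of at most 0.225 + 0.55 = 77.5%.

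**The case against.** A reader might infer that the plan counts harmful changes and misplaced confidence as benefit, or that the study would present a less safe device as the better one. The documents do not support either reading.

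- G2 sets no score, test or success criterion for these endpoints. It calls them exploratory and presents a table.
- The table keeps the direction of each change. It does not reduce to a single count of impact.
- Sensitivity and NPV are reported against histology for each method, so a device with 50% sensitivity would be visible there.
- Because F2 has every Lugol's-abnormal site biopsied regardless, a switch to no biopsy does not remove the tissue diagnosis at that site.

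The illustration is also open to attack. The pre-software plan in F2 is recorded after the clinician's own microendoscope read, so some sites may already be no biopsy or treat. F2 says only that the software may influence the plan. The prevalence is assumed.

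All of this stands, and it limits the size of the point. What remains is narrower. The method-level measures describe reads; the post-software plan and confidence are separate recorded variables, and no planned analysis compares either with histology. Direction without correctness does not show whether the software improved a decision.

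**Conclusion.** The point holds as a limitation of two exploratory analyses. As defined in section D and tabulated in G2, clinical impact and confidence can show that the software changed something and in which direction, but not whether the change was right. The tables cannot by themselves support the hypotheses of increased impact and confidence.

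The effect on the G2 tables cannot be quantified, because the documents give no rate of plan change from the pre-software microendoscope read. The 22% to 54% range is an illustration resting on assumed prevalence, an all-biopsy starting plan and full adherence to the software. The conclusion does not depend on it; it follows from the definition and the layout of the table.

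Severity is minor. The primary endpoint, sample size and power are unaffected, and no safety failing for participants follows from this point.

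**What to change.** Amend G2 as follows, for Lugol's-abnormal sites with histology:

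1. Present the pre/post-software plan table separately for histologically neoplastic and non-neoplastic sites.
2. Report favourable changes (no biopsy to biopsy or treat at neoplastic sites; biopsy or treat to no biopsy at benign sites) and unfavourable changes (the reverse), each with a 95% confidence interval. List switches between biopsy and treat separately without scoring them. These are analysis labels, not rules for managing patients.
3. Report pre- and post-software confidence (high/low) by whether the diagnosis was correct. State which diagnosis is meant after the software, since section D refers to confidence in the software's diagnosis and F2 to the endoscopist's confidence.
4. Use intervals that allow for several sites per patient, for example by resampling patients.
5. Keep the expert/novice split descriptive. A 3 × 3 plan table by histology and by experience has 36 cells for about 100–150 sites, or roughly 3 to 4 sites per cell.
6. Base any statement about impact on favourable versus unfavourable changes.

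The cost is wording in G2 and some programming. Reads, plans, confidence and histology are already collected at these sites, so no new data, procedure or sample-size change is needed. The tables could be produced afterwards from the same data, but specifying them before results are seen avoids selective reading.
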